12.6.2 Physical Examination and Adverse Events

Physical examination results will be summarized by frequency of presence of abnormalities in body system (beyond the DMD diagnosis) and in particular any changes in the physical examination over time.

TEAEs will be summarized by treatment group. Coding will be done by system organ class and preferred term (using the Medical Dictionary for Regulatory Activities [MedDRA]). Level of severity will be assessed using the CTCAE grading system.

Summaries will include:

- Summaries at the participant level
 - How many participants had any TEAE, any SAE, highest severity of TEAE within a participant across all infusions, highest relationship level of TEAE within a participant across all infusions, highest intervention level regarding investigational product (e.g., discontinued, vs. infusion interruption vs. no interruption in infusions), and worst outcome within a participant (e.g., AE did not resolve and has a permanent effect).
- Summary at the event level
 - Summaries will be done using the MedDRA coding by events and overall, summarizing by system organ class and preferred term, by relationship to investigational product, severity, intervention, and outcome.

Listings tables will be provided for all AEs.

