The maximum plasma concentration and area under the curve (AUC_{0-t}) values increased in a dose-dependent manner, and the t_{1/2} value was between 1.52 and 1.84 hours.

Distinct exon 53 skipping efficiency by reverse transcriptase polymerase chain reaction (RT-PCR), positive dystrophin fibers by immunofluorescent staining, and dystrophin protein expression by Western blot were detected in one patient in Cohort 3, who was the largest patient enrolled in the cohort and hence received a largest absolute dose of viltolarsen injection that was administered in the study.

Phase 2 Trials

Study NS065/NCNP01-P1/2, Study NS-065/NCNP-01-201, and Study NS-065/NCNP-01-202 of viltolarsen were completed. Results for all studies are detailed below.

Study NS065/NCNP01-P1/2

Study NS065/NCNP01-P1/2 is a Phase 1/2 study of viltolarsen injection conducted in Japan.

This was a multi-center, parallel-group, open-label, 24-week study. Participants received weekly IV administration of viltolarsen injection 250 mg (40 mg/kg and 80 mg/kg) over 24 weeks. The primary efficacy endpoint of this study is dystrophin protein expression as measured by Western blot, immunofluorescence staining, and RT-PCR. Sixteen DMD patients amenable to exon 53 skipping, aged 5 to <18 years were enrolled.

Viltolarsen injection was well tolerated in up to the highest administered dose of 80 mg/kg; no SAEs were observed, one SAE (upper respiratory tract infection, Grade 2, not-related to drug) was reported, and no patients discontinued study drug administration as a result of an AE.

Adverse events included 84 Grade 1 AEs in 10 patients, 11 Grade 2 AEs in 5 patients, and no Grade 3 AEs. The Grade 2 AEs included nasopharyngitis, and eczema, each in 2 patients, and miliaria (a common disorder of eccrine sweat glands), pharyngitis, ejection fraction decreased, ligament sprain, and urine protein present, each in 1 patient. No evidence for immunogenicity

was found in any Phase 1/2 study participants, as no anti-viltolarsen or anti-dystrophin antibodies were detected in DMD patients receiving 40 or 80 mg/kg viltolarsen injection in this study.

Under the conditions of this clinical trial, viltolarsen injection was safe and well tolerated up to 80 mg/kg, the highest dose in this study.

Study NS-065/NCNP-01-201

Study NS-065/NCNP-01-201 is a Phase 2 study conducted in the US and Canada.

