12 PLANNED STATISTICAL METHODS

12.1 General Considerations

The statistical analyses described in this section will be performed as further outlined in the statistical analysis plan (SAP), which will be finalized prior to database lock. The SAP will supersede the protocol if there are any differences between the two documents in the plans for data analysis and the differences will be noted in the SAP. The SAP will be included as an appendix in the clinical study report for this protocol. Statistical analyses will be performed using SAS 9.2 or higher.

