12.6 Safety Assessments

Safety analyses will be performed using the safety population. All safety assessments will be based on actual treatments received by participants and are detailed in the protocol and statistical analysis plan.

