12.6.3 Concomitant Medications and/or Other Treatments

Glucocorticoids, which are required as part of the inclusion criteria, will be summarized by type of GC (prednisone vs. deflazacort), by schedule (daily vs. any other), and by treatment.

Participants are required not to change the GC dose while on study. Any changes in doses or schedule will be listed.

Other concomitant medications will be summarized by ATC class and preferred term. Each medication will be counted once within a participant using it, regardless of the number of times it was reported on the eCRFs. The summaries will note new medications or supplements vs. those already given at baseline and study entry. Any other treatment, surgeries, will be listed and described; however, those are expected to be few without a need to be summarized using tables.

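### Protocol section 12.6.2 tabulates specific adverse events at event level only, so its tables give no number or percentage of boys per arm with any given event

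*Combined protocol and SAP*

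**What the plan says.** Section 12.6.2 states that "TEAEs will be summarized by treatment group" and then sets out two blocks.

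- **Participant level.** This block begins "How many participants had any TEAE, any SAE, highest severity of TEAE within a participant across all infusions" and goes on to highest relationship, highest intervention level and worst outcome. Every row is an overall row; none is split by system organ class or preferred term.
- **Event level.** Class and term appear only here: "Summaries will be done using the MedDRA coding by events and overall, summarizing by system organ class and preferred term". The block then adds relationship, severity, intervention and outcome.

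The section closes with "Listings tables will be provided for all AEs". It gives no rule for counting a boy who reports the same term more than once. Section 12.6.3 does give one for concomitant medications: "Each medication will be counted once within a participant using it, regardless of the number of times it was reported on the eCRFs".

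Two other statements bear on this. Section 12.6 says that the safety assessments "are detailed in the protocol and statistical analysis plan", and section 12.1 says "The SAP will supersede the protocol if there are any differences between the two documents in the plans for data analysis". The supplied documents contain no separate SAP text on adverse events.

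**The concern.** Safety and tolerability is a stated secondary objective (section 3). For a named event, the natural comparison is how many of the 37 boys in each arm had it. An event count cannot tell ten boys with one event each from one boy with ten. Adverse events are assessed at every visit or contact (section 9.13) over 48 weekly infusions, so a boy has many occasions to report the same term again.

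The error can go either way. A real excess of affected boys can be matched, and so hidden, by one boy's repeats in the other arm. Equally, one boy's repeats can look like a drug effect. The point concerns the class and term tables only; overall tolerability is already compared boy against boy.

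**Working it through.** **1. Denominator.** Section 12.2 gives a mean difference of 0.05, SD 0.075, two-sided alpha 0.05, power 0.80 and 1:1 allocation. The standardised difference is 0.05/0.075 = 0.667. The two-sided unpaired t-test needs 36.3 per arm, rounded up to 37, so 74 in total. This matches the plan. (The normal approximation gives 36 per arm, 72 in total.) The safety tables therefore compare about 37 boys with 37.

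**2. What the planned tables hold.**

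| Summary by arm | Any event, overall | By class and term |
|---|---|---|
| Boys, n (%) | planned (12.6.2) | not stated |
| Events | planned (12.6.2) | planned (12.6.2) |
| Count-once rule, adverse events | not needed | not stated |
| Count-once rule, medications | not applicable | stated (12.6.3) |

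**3. Illustrations at 37 per arm.** The counts are assumed; the documents give no frequencies by term for this trial.

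- *Hiding a difference.* Eight viltolarsen boys have one event each and one placebo boy has eight. Events: 8 v 8. Boys: 8/37 = 21.6% v 1/37 = 2.7%.
- *Creating a difference.* One viltolarsen boy has the term 12 times and one placebo boy has it once. Events: 12 v 1. Boys: 1/37 v 1/37, 2.7% each.

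**4. How often chance alone misleads.** Assumptions: no true difference; each boy is affected with probability 0.20; an affected boy has 1 + R events, where R has mean m. R is either Poisson (all affected boys share one rate) or gamma-Poisson with shape 1 (rates vary between boys). An imbalance is counted when the larger arm total is at least twice the smaller. Each setting used 40,000 simulated trials. The expected number of affected boys per arm is 37 × 0.20 = 7.4; with m = 6 the expected number of events is 7.4 × 7 = 51.8.

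| Mean repeats m | Spread of repeats | Two-fold imbalance, events | Two-fold imbalance, boys |
|---|---|---|---|
| 6 | Poisson | 20% | 20% |
| 0.22 | Poisson | 23% | 20% |
| 3 | gamma-Poisson, shape 1 | 33% | 20% |
| 6 | gamma-Poisson, shape 1 | 34% | 20% |

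In the last row the most affected boy supplies on average 36% of his arm's events. With m = 1 the event figure runs from 24% to 33% across Poisson and gamma shapes down to 0.5. With m = 6 and shape 0.5 it would reach 43%, but nothing in the documents points to so skewed a spread.

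**5. Source of the low value of m.** Section 2.3.3 reports 11 Grade 2 events in the Phase 1/2 study and names two terms seen in 2 patients each and five seen in 1 patient each. That is 2 × 2 + 5 × 1 = 9 patient-term pairs, and 11/9 = 1.22 events per pair, so 0.22 repeats. These are few patients over 24 weeks, at Grade 2 only, so recurrence over 48 weeks could be higher.

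**The case against.** The strongest reply is that the text is incomplete rather than wrong. The list in 12.6.2 is introduced in open terms, the word overall in the event-level sentence is undefined, and table-level counting rules are the kind of detail left to a SAP that takes precedence. A reader might infer that the final report will carry event counts and nothing else for specific events. The documents do not support that; they show only that the protocol states no participant-level table by class or term. That narrower statement stands, because nothing supplied fills the gap.

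The listings are also a real mitigation. With 74 boys, a recurring event can be traced to one boy. But a listing is not an incidence by arm, and the reader would have to build the table himself.

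Two further inferences should be resisted. Section 2.3.3 reports "Adverse events included 84 Grade 1 AEs in 10 patients, 11 Grade 2 AEs in 5 patients, and no Grade 3 AEs", which might be read as evidence of recurrence. It counts all events across all terms, so it shows many events per boy and not repeats of one term. The Grade 2 figures in the same section suggest low recurrence. A reader might also argue from false-positive rates, testing event totals as if events were independent. The planned adverse-event summaries are descriptive and no between-arm test is specified, so such p-values have no counterpart in the plan and are left out here.

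**Conclusion.** The point holds for the class and term tables as the protocol is written. Following section 12.6.2 to the letter yields no number or percentage of boys per arm with any specific event, and event counts can mislead in either direction.

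The size is uncertain. With 20% of boys affected and no true difference, a chance two-fold imbalance occurs in about 20% to 34% of trials on events against about 20% on boys. The upper figure needs a mean of six repeats and rates that vary between boys (gamma shape 1). With equal rates the gap vanishes, and at the recurrence suggested by the Phase 1/2 Grade 2 data it is about three percentage points. The case for change rests mainly on the missing incidence by arm. Efficacy inference and sample size are untouched.

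**What to change.** In section 12.6.2, and in the SAP, state that the system organ class and preferred term tables show, for each arm, the number and percentage of boys with at least one TEAE. Count each boy once per class and once per term; where the table is crossed with severity or relationship, count him at his highest level. Do the same for treatment-emergent SAEs. Keep the number of events as a second column, since recurrence is itself of interest.

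The cost is a few sentences of wording and one extra column or table from data already collected and coded. Sites and participants are unaffected.

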12.6.3 Concomitant Medications and/or Other Treatments

Glucocorticoids, which are required as part of the inclusion criteria, will be summarized by type of GC (prednisone vs. deflazacort), by schedule (daily vs. any other), and by treatment.

Participants are required not to change the GC dose while on study. Any changes in doses or schedule will be listed.

Other concomitant medications will be summarized by ATC class and preferred term. Each medication will be counted once within a participant using it, regardless of the number of times it was reported on the eCRFs. The summaries will note new medications or supplements vs. those already given at baseline and study entry. Any other treatment, surgeries, will be listed and described; however, those are expected to be few without a need to be summarized using tables.

12.6.3.1 Antibodies and Pharmacokinetics

Antibodies and PK concentrations will be summarized by treatment group over time. PK concentrations may be summarized at a later date.

12.7 Pharmacokinetic Endpoints and Analysis

Population PK analysis will be presented in a separate report.

12.8 Interim Analyses

Interim analysis is planned when approximately 90% of participants are enrolled in the study. An additional unblinded review and re-estimation will be performed when approximately 50 participants have completed the Week 49 evaluations for the primary outcome measure. At these 2 time points, an unblinded data review will be conducted, which will include review by the DSMB. Based on this review, the DSMB will make a recommendation to the sponsor for possible sample size re-estimation, i.e., the additional number of participants to be enrolled to increase the conditional power to an acceptable level.

Denne (Denne, 2001) described the sample size re-estimation procedure for the group sequential test by using the conditional power without inflating the type I error rate for the interim analyses. At the point at which the sample size re-estimation is being made for the interim analyses, the test statistic z_1 is observed. The conditional power is the probability of rejection H_0 on the basis that $Z_2 \geq c_2$ given $Z_1 = z_1$, which is denoted by $CP_\theta(n_2, c_2|z_1)$. The conditional power is given by:

$$CP_\theta(n_2, c_2|z_1) = 1 - \Phi \left[\frac{c_2\sqrt{n_2} - z_1\sqrt{n_1} - \frac{(n_2-n_1)}{\sqrt{2}\sigma^2}\theta}{\sqrt{n_2 - n_1}} \right]$$

where n_1 is the sample size per treatment group at the interim analyses, the true difference in mean response θ is estimated by the current sample mean difference δ , and σ^2 is estimated by the current sample within group variance s^2 . The re-estimated sample size per treatment group n_2 is obtained by solving the conditional power be at least 80% power as defined in the sample size determination. The re-estimated total sample size is given by $n^* = 2n_2$.

To preserve study integrity, a small alpha of 0.001 will be spent at the second re-estimation resulting in the overall significance level to be 0.049 at the final stage.

If the re-estimated total sample size from the interim analyses is smaller than the planned total sample size of 74, the sample size adjustment will not be needed. If the re-estimated total

sample size is larger than the planned total sample size, the sample size may be increased up to a maximum target sample size of 100.

12.9 Handling of Missing Data

Every effort will be made to collect all data. However, despite best efforts, missing or incomplete data may be reported. All missing or partial data will be presented in the participant data listing, as they are recorded on the eCRF.

Participants lost to follow-up or withdrawn will be included in statistical analyses up to the point of their last evaluation. Unless otherwise specified, no imputation of values for missing data will be performed. Of note, since participants with DMD are expected to decline over time, imputing efficacy parameters by last value carried forward mostly biases towards participants appearing stronger or faster than they are, since it carries forward potentially a better value than the value at the time of the missed observation. Therefore, for this study, we will summarize how much data are missing, but do not expect to need to impute any data to accomplish the analyses as described. Details of handling missing data will be described in the SAP.

Appendix 3 Administrative Considerations

Investigators

The investigator must agree to the responsibilities and obligations listed below, as specified by the appropriate FDA/Health Canada regulatory requirements or International Council for Harmonisation/Good Clinical Practices (ICH/GCP) guidelines:

- Agree to conduct the study in accordance with the relevant current protocol;
- Agree to personally conduct or supervise the described investigation(s);
- Agree to inform any participants, or persons used as controls, that the investigational products are being used for investigational purposes and ensure that the requirements relating to obtaining informed consent and IRB/IEC review and approval are met;
- Agree to report adverse experiences that occur during the course of the investigation(s);
- Read and understand the information in the Investigator’s Brochure, including the potential risks and side effects of the investigational product;
- Ensure that all associates, colleagues, and employees assisting in the conduct of the study are informed about their obligations in meeting the above commitments;
- Maintain adequate and accurate records and make those records available for inspection;
- Ensure that an IRB/IEC will be responsible for the initial and continuing review and approval of the clinical investigation;
- Agree to promptly report to the IRB/IEC all changes in the research activity and all unanticipated problems involving risks to participants or others;
- Agree to not make changes in the research without IRB/IEC approval, except where necessary to eliminate apparent hazards to participants; and
- Comply with all other requirements regarding the obligations of clinical investigators and all other pertinent requirements.

Refer also to:

- FDA Regulations Related to Good Clinical Practice (GCP) and Clinical Trials:
<http://www.fda.gov/oc/gcp/regulations.html>
- Guidance and Information Sheets on GCP in FDA-Regulated Clinical Trials:
<http://www.fda.gov/oc/gcp/guidance.html>

- Guidance for IRBs and Clinical Investigators:
<http://www.fda.gov/oc/ohrt/irbs/default.htm>
- Guidance for Industry - E6 Good Clinical Practice: Consolidated Guidance
<http://www.fda.gov/cder/guidance/959fnl.pdf>

Informed Consent, Protected Health Information (PHI) and Confidentiality

Informed Consent

The ICF, assent form, and consent process must comply with US 21CFR Part 50 and local laws. The ICF/Assent Form will document the study-specific information provided to the participant by the investigator or designee and the participant's/legal guardian's agreement to participate in the study.

The investigator, or designee (as described on Delegation of Authority log), must explain in terms understandable to the participant, the purpose and nature of the study, the study procedures, anticipated benefits, potential risks, the possible adverse effects and any discomfort participation in the study may involve. Each participant must provide a signed and dated ICF before any study related procedures are performed. In the case of a participant who is incapable of providing informed consent, the investigator or designee must obtain a signed and dated ICF from the participant's legal guardian.

Minors, who are not legally capable of giving informed consent, may possess the ability to assent or dissent to participation in the study. The investigator, or designee should explain the study and study procedures to the minor in as much detail as the minor is able to comprehend.

IRB/IEC-approved, age-appropriate Assent Forms must be obtained from minor participants as required by local laws and governing IRBs/IECs.

Confidentiality

Authority regulations (FDA, Health Canada, or other national and local health authorities) require the sponsor or the sponsor's authorized representative to inspect all study documents and records maintained by the investigator, including but not limited to medical records (office, clinic, or hospital) for the participants in this study. These regulations also allow the sponsor's records to be inspected by authorized representatives of the regulatory authorities. The names and identities of all research participants will be kept in strict confidence and will not appear on

eCRFs or other records provided to or retained by the sponsor or the sponsor’s authorized representative. Participant confidentiality will be respected during review of source documents by monitors, auditors and other sponsor representatives. Review procedures will adhere to regulatory requirements and professional standards for confidentiality. Names and identities of participants can be protected by de-identifying (i.e., “blacking-out”) participant’s name and replacing the name with the participant’s study identification number. The ICF must include appropriate statements explaining these requirements.

Protected Health Information (PHI)

Information on maintaining participant confidentiality in accordance with US and local patient privacy regulations must be provided to each participant/legal guardian as part of the informed consent process, either as part of the ICF or as a separate signed HIPAA consent. The investigator or designee must explain to each participant that for the evaluation of study results, the participant’s PHI obtained during the study may be shared with NS Pharma and its designees, regulatory agencies and IRBs/IECs. As the study sponsor, NS Pharma will not use the participant’s PHI or disclose it to a third party without applicable participant authorization. It is the investigator’s responsibility to obtain written permission to use PHI from each participant/legal guardian. If a participant or participant’s legal guardian withdraws permission to use PHI, it is the investigator’s responsibility to obtain the request in writing and ensure that no further data is collected on the participant. Any data collected up to the point of HIPAA consent withdrawal may be used in analysis of the study results.

Study Administrative Structure

Institutional Review Board/Independent Ethics Committee Approval

Before initiation of the study, the investigator must obtain approval or favorable opinion of the research protocol, informed consent form, and any material related to participant recruitment from an IRB or IEC complying with the provisions specified in 21 CFR Part 56 and applicable pertinent state and federal requirements of each participating location, including ICH and GCP guidelines.

Institutional Review Boards and IECs must be constituted according to the applicable laws. It is the responsibility of each clinical site to submit the protocol, Investigator's Brochure, participant informed consent, participant recruitment materials (if applicable), and other documentation as required by the IRB/IEC for review and approval. A copy of the written approval must be provided to NS Pharma.

The documentation should clearly mention the approval/favorable opinion of the protocol, the participant informed consent form, and participant recruitment materials (if applicable), including respective version dates. The written approval and a list of the voting members, their titles or occupations, and their institutional affiliations must be obtained from the IRBs/IECs and provided to NS Pharma (or its authorized CRO) prior to the release of clinical study supplies to the clinical site and commencement of the study. If any member of the IRB/IEC has direct participation in this study, written notification regarding his or her abstinence from voting must also be obtained.

Clinical sites must adhere to all requirements stipulated by their respective IRB/IEC. This includes notification to the IRB/IEC regarding: protocol amendments, updates to the participant informed consent, recruitment materials intended for viewing by participants, IND Safety Reports, serious and unexpected adverse events, reports and updates regarding the ongoing review of the study at intervals specified by the respective IRB/IEC, and submission of final study reports and summaries to the IRB/IEC.

It is the responsibility of each clinical site to submit information to the appropriate IRB/IEC for annual review and annual re-approval.

The investigator must promptly inform their IRB/IEC of all SAEs or other safety information reported from the participant or NS Pharma or its authorized CRO.

Protocol Amendments

Any changes to the study that arise after approval of the protocol must be documented as protocol amendments. Protocol amendments that are deemed substantial (e.g., affecting the safety of the participant, the scope of the study, and/or the scientific quality) will be submitted to regulatory authorities and/or to the IEC/IRB as appropriate. For substantial amendments, the changes will become effective only after approval by the Sponsor, the responsible Investigator, IEC/IRB, and competent authorities. All other amendments (i.e., non-substantial or administrative amendment) will be documented in the Trial Master File.

Ethical Conduct of the Study

The investigator agrees, when signing the protocol, to adhere to the instructions and procedures described in the protocol and conduct the study in accordance with the CFRs (21 CFR Parts 11, 50, 54, 56, 312, 314, and 320) and local regulations, which originate from the ethical principles laid down in the current revision of the Declaration of Helsinki, GCPs, and policies and procedures as outlined by the ethical requirements for IRB/IEC review and informed consent forms.

The investigator agrees to allow monitoring and auditing of all essential clinical study documents by NS Pharma or its authorized representatives and inspection by the FDA or other appropriate regulatory authorities. Monitoring and auditing visits by NS Pharma or authorized designee will be scheduled with the appropriate staff at mutually agreeable times periodically throughout the study.

The investigator will assure proper implementation and conduct of the study, including those study-related duties delegated to other appropriately qualified individuals. The investigator will assure that study staff cooperates with monitoring and audits and will demonstrate due diligence in recruiting and screening study participants. The investigator must sign and return to NS Pharma (or its authorized CRO) the “Study Acknowledgment” page and provide a copy of current curriculum vitae.

Study Monitoring

The investigator agrees to allow direct access to all essential clinical study documents for the purpose of monitoring and/or auditing by NS Pharma or its authorized representatives and inspection by the appropriate regulatory authorities.

NS Pharma (or its authorized CRO) has the obligation to follow this study closely to ensure that the study is conducted in accordance with the protocol, ICH and GCP regulatory requirements, the CFRs, FDA, and the current Declaration of Helsinki throughout its duration by means of personal visits to the investigator's facilities and other communications.

These visits will be conducted to evaluate the progress of the study, verify the rights and well-being of the participants are protected, and verify the reported clinical study data are accurate, complete, and verifiable from source documents. This includes review of informed consent forms, results of tests performed as a requirement for participation in this study, and any other medical records (e.g., laboratory reports, clinic notes, investigational product disbursement log, pharmacy records, participant sign-in sheets, participant-completed questionnaires, telephone logs, ECGs) required to confirm information contained in the eCRFs.

A monitoring visit should include a review of the essential clinical study documents (regulatory documents, case report forms, medical records and source documents, investigational product disposition records, participant informed consent forms, etc.) as well as discussion on the conduct of the study with the investigator and staff.

The monitor should conduct these visits as frequently as appropriate for the clinical study. The investigator and staff should be available during these visits for discussion of the conduct of the study as well as to facilitate the review of the clinical study records and resolve/document any discrepancies found during the visit.

All monitoring activities will be reported and archived. In addition, monitoring visits will be documented at the clinical site by signature and date on the study-specific monitoring log.

Details of monitoring procedures will be described in the study monitoring plan.

On-Site Audits

Representatives of NS Pharma or its authorized clinical quality assurance group may visit a clinical site at any time during the study to conduct an audit of the study in compliance with regulatory guidelines and company policy. These audits will require access to all study records, including source documents, for inspection and comparison with the eCRFs. Participant privacy must be respected. The investigator and clinical site personnel are responsible for being present and available for consultation during routinely scheduled site audit visits conducted by NS Pharma or its authorized representative.

The clinical study may also be inspected by the FDA (or other regulatory authorities) to verify that the study was conducted in accordance with protocol requirements, as well as the applicable regulations and guidelines.

In the event the investigator is contacted by regulatory authorities who wish to conduct an inspection of the clinical site, the investigator will promptly notify NS Pharma (or its authorized CRO) of all such requests and will promptly forward a copy of all such inspection reports.

Case Report Forms

Access to eCRFs will be provided to the clinical site. As part of the responsibilities assumed by participating in the study, the investigator agrees to maintain adequate case histories for the participants treated as part of the research under this protocol. The investigator agrees to maintain accurate source documentation and eCRFs as part of the case histories.

Study records are comprised of source documents, eCRFs, and all other administrative documents (e.g., IRB/IEC correspondence, clinical study materials and supplies shipment manifests, monitoring logs, and correspondence). A study-specific binder will be provided with instructions for the maintenance of study records.

A completed eCRF must be submitted for each participant who receives investigational product, regardless of duration. All supportive documentation submitted with the eCRF, such as laboratory or hospital records, should be clearly identified with the study and participant number. Any personal information, including participant name, should be removed or rendered illegible

to preserve individual confidentiality. The eCRF should not be used as a source document unless otherwise specified by NS Pharma.

It is essential that all dates appearing on NS Pharma participant data collection forms for laboratory tests, cultures, etc., be the dates on which the specimens were obtained, or the procedures performed. The eCRFs will be electronically signed by the investigator and dated as verification of the accuracy of the recorded data. All data collection forms should be completed within 48 hours following the evaluation.

Data reflecting the participant's participation with the investigational product under investigation are to be reported to NS Pharma. The data are to be recorded on the eCRFs and/or other media provided or approved by NS Pharma.

Details for completing the eCRF are provided in the eCRF completion manual for this study.

Source Documents

Source documentation is defined as any hand written or computer-generated document that contains medical information or test results that have been collected for or in support of the protocol specifications (e.g., laboratory reports, clinic notes, investigational product disbursement log, pharmacy records, participant sign-in sheets, participant completed questionnaires, telephone logs, x-rays, and ECGs). All draft, preliminary, and pre/final iterations of a final report are also considered to be source documents (e.g., faxed and hard copy of laboratory reports, faxed and hard copy of initial results, and final report).

Authority regulations require the sponsor (or the sponsor's authorized representative) to inspect all documents and records to be maintained by the investigator, including but not limited to, medical records (office, clinic, or hospital) for the participants in this study. These regulations also allow the sponsor's records to be inspected by authorized representatives of regulatory authorities. The investigator will permit study-related monitoring, audits, IRB/IEC review, and regulatory inspections by providing direct access to source data/documents. Direct access includes permission to examine, analyze, verify, and reproduce any records and reports that are important to the evaluation of a clinical study.

Record Retention

In compliance with the ICH/GCP guidelines, the investigator/institution agrees to retain and maintain all study records that support the data collected from each participant, as well as all study documents as specified in ICH/GCP, Section 8 Essential Documents for the Conduct of a Clinical Trial. Retention of study documents will be governed by the Clinical Study Agreement between the sponsor and Institution.

Study documents (including eCRFs, source documents, clinical drug disposition records, signed participant informed consent forms, adverse event reports, and other regulatory documents) as required by the applicable regulations, must be maintained for 15 years after a marketing application is approved for the drug for the indication for which it is being investigated; or, if no application is to be filed or if the application is not approved for such indication, until 2 years after the investigation is discontinued and the FDA is notified.

It is the responsibility of NS Pharma or authorized CRO to inform the investigator/institution as to when these documents no longer need to be retained.

Publication and Disclosure Policy

All information derived from this clinical study will be used by NS Pharma (or designee) and therefore, may be disclosed by NS Pharma (or designee) as required to other clinical investigators, to the FDA, and to other government agencies, or in connection with intellectual property filings or publications. Details of disclosure of study information are provided in the investigator's written clinical study agreement with NS Pharma.

The results of the study will be reported in a clinical study report (CSR) prepared by NS Pharma (or designee), which will contain eCRF data from all clinical sites that conducted the study.

NS Pharma shall have the right to publish data from the study without approval from the investigator. All publications (e.g., manuscripts, abstracts, oral/slide presentations, book chapters) may only be prepared through cooperation between NS Pharma (or designee) and the study investigator(s). If an investigator wishes to publish information from the study, a copy of the manuscript must be provided to NS Pharma for review in accordance with the provisions of such investigator's written agreement with NS Pharma (or designee) before submission for

publication or presentation. If requested by NS Pharma in writing, the investigator will withhold such publication in accordance with the provisions of such agreement.

Authorship of any publications resulting from this study will be determined on the basis of the Uniform Requirement for Manuscripts Submitted to Biomedical Journals International Committee of Medical Journal Editors (ICMJE) Recommendations for the Conduct of Reporting, Editing, and Publications of Scholarly Work in Medical Journals, which states:

Authorship credit is to be based on: (1) substantial contributions to conception and design, acquisition of data, or analysis and interpretation of data; (2) drafting the article or revising it critically for important intellectual content; (3) final approval of the version to be published; and (4) agreement to be accountable for all aspects of the work in ensuring that questions related to the accuracy or integrity of any part of the work are appropriately investigated and resolved.

Authors need to meet conditions 1, 2, 3, and 4.

When a large, multi-center group has conducted the work, the group is to identify the individuals who accept direct responsibility for the manuscript. These individuals must fully meet the criteria for authorship defined above.
